### **Planned analyses**

#### *Primary analysis*

To answer the main research question, a linear regression (or ANCOVA) will be performed to compare the estimated mean scores at 1 month between the two randomization groups after adjustment for the baseline knowledge score. For subjects for whom the knowledge score could not be obtained at post-test, we will use the baseline value as post-test value in order to avoid missing data. The threshold of statistical significance under the null hypothesis is set with a type I error,  $\alpha < 0.05$

The primary analysis will be carried out by a statistician from the Methodological Support Unit of the HUG Clinical Research Centre, who will be commissioned by the investigator once the data of the last patient included have been collected.

## Secondary analyses

Comparisons of continuous secondary outcomes between the two randomization groups will be made by Student's t tests; comparisons of categorical or ordinal qualitative secondary outcomes will be made using a Chi-2 test or Fisher's exact test (in case of smaller expected number <5). The analyses will be carried out by a statistician from the methodological support unit of the HUG clinical research center on a specific and recognized computer software.

## Deviation(s) from the original statistical plan

Any deviation from the original statistical plan will be noted and explained in the final report.

### 5.2 Handling missing data and dropouts

The status of a longitudinal study is related to a high degree of loss to follow-up. In subjects for whom the knowledge score could not be obtained at post-test, we will use the baseline value as the post-test value in order to avoid missing data.

## 6 REGULATORY AND SAFETY ASPECTS

### 6.1 Local regulations / Helsinki declaration

This study is conducted in accordance with the protocol, the current version of the Declaration of Helsinki, the ICH-GCP. If the clinical trial is not conducted in accordance with the ICH-GCP, the above paragraph must be adapted accordingly (ClinO Art. 5, Abs 2), to the HRA as well as to other locally relevant legal and regulatory requirements.

### 6.2 Adverse events (serious)

An adverse event (AE) is any untoward medical occurrence in a patient or clinical study subject that is not necessarily causally related to the trial procedure. Thus, it can be any adverse or unintended finding, symptom, or illness associated over time with a trial procedure, whether or not it is related to the trial procedure.

A serious adverse event (SAE) (ClinO, s. 63) is any untoward medical event that

- results in death or is life threatening,
- requires hospitalization or extension of an existing hospitalization,
- results in a persistent or significant disability or impairment, or
- causes a birth defect or congenital malformation.

The investigator and sponsor assess the causality of the event to the trial intervention (see table below based on terms given in the ICH E2A guidelines).

Any event assessed as possibly, probably, or definitely related is classified as related to the trial intervention (Table 3)

**Table 3: Description of Adverse Drug Event Types**

Relationship	Description
--------------	-------------

Some	Temporal relationship Improvement after stopping treatment*. Recurrence after resumption of treatment (or other evidence of the presence of the drug)
Probable	Temporal relationship Improvement after stopping treatment*. No other obvious cause
Possible	Temporal relationship No other obvious cause
Improbable	Any evaluable reaction that does not meet the above conditions.
Not related	A causal relationship can be excluded.
* Improvement after the "unchallenge" is only taken into account if it applies to the reaction	

The investigator and sponsor rate the severity of the event as mild, moderate or severe. Mild means the complication is tolerable, moderate means it interferes with daily activities, and severe means it makes daily activities impossible.

### Reporting of SAEs (see ClinO, Art. 63)

All AEs are documented and reported immediately (within 24 hours) to the study sponsor.

If it cannot be excluded that the SAE in Switzerland is attributable to the intervention under study, the investigator reports it to the Ethics Committee via BASEC within 15 days.

### Monitoring of serious adverse events

Any patient with an SAE who has agreed to participate in the study will be reassessed by the investigator to see if they still meet the inclusion criteria. If the patient no longer meets the criteria, they will be removed from the study.

The risk of an SAE being attributable to our intervention is very low because it does not directly impact patient care.

Each participant who presented an SAE attributable or not to the studied procedure will be analyzed by the investigator. The investigator will attempt to identify the reason for the SAE in each case by consulting the patient's physicians and will document it in the patient's CRF. If the SAE is caused by a drug, the investigator will declare a pharmacovigilance announcement.

### 6.3 (Periodic) Safety Report

An annual safety report will be submitted once a year to the local ethics committee by the investigator (ClinO, Art. 43 Abs) if applicable for this type of study.

### 6.4 Amendments

Substantial changes in study set-up and organization, protocol, and relevant study documents are subject to approval by the Ethics Committee prior to implementation. In emergency circumstances, deviations from the protocol to protect the rights, safety and welfare of human subjects may be made without prior approval of the Ethics Committee. Such deviations should be documented and reported to the Ethics Committee as soon as possible.

A list of all non-substantive changes will be submitted annually to the appropriate EC with the annual safety report

## 6.5 (Premature) study termination

The sponsor and the principal investigator may terminate the study prematurely under certain circumstances, such as

- Ethical issues,
- Insufficient recruitment of participants,
- When participant safety is in doubt or at risk (e.g., when the benefit-risk assessment is no longer positive),
- Changes in accepted clinical practice that make it unwise to continue the study, or
- Early evidence of harm or benefit from the experimental intervention.

In the event of the regular termination of the study, the ethics committee is informed via BASEC within 90 days (ClinO, art. 38).

In the event of premature termination or interruption of the study, the ethics committee is informed via BASEC within 15 days (ClinO, art. 38).

## 6.6 Insurance

In case of damage or injury related to the study, the University Hospitals of Geneva is liable for compensation, except for claims resulting from fault or gross negligence.

# 7 OTHER ASPECTS

## 7.1 Other ethical considerations

This trial will be able to generate results that will be important in the field of patient education. We want to evaluate whether the intervention of a hospital pharmacist with heart failure patients on their knowledge can have a positive impact on their health behavior. Offering patients the opportunity to access information on these high value-added drugs during their hospital stay seems to us to be essential in order to ensure the best possible long-term adherence to taking these drugs. If the results of this study show that the patient's knowledge, beliefs and adherence to treatment are improved, then these teaching interviews could be offered to all patients with heart failure in the hospital. This will allow the deployment of other interventions for other chronic conditions. If the results are negative, the reasons for this failure will be identified and evaluated in order to readjust the pharmacist's interventions to improve patients' knowledge and therapeutic adherence.

This study offers any hospitalized patient with heart failure who is being treated with medication a new tool to improve their health knowledge while receiving quality care from the hospital. This care will not be altered by this study.

## 7.2 Risk-benefit assessment

There is no risk of harm to patients by participating in this study.

The pharmaceutical intervention does not present any risk to the patient in the sense that it does not alter the patient's therapeutic management in any way. The project does not discourage any treatment or any change in the usual management of the patient by the medical and nursing staff.

This project even reinforces the care of the hospital medical and nursing team by educating the patient on his or her pathology and follow-up. It gives them the tools to take ownership of their disease and become autonomous in their follow-up. The participants will be able to benefit from the trial.

## 8 QUALITY CONTROL AND DATA PROTECTION

### 8.1 Quality measurement

For quality assurance, the sponsor, the ethics committee or an independent trial monitor may visit the research sites. Direct access to source data and all study-related files is granted on these occasions. All parties involved keep participant data strictly confidential.

### 8.2 Data recording and source data

All baseline data will be assessed with the medical record consultation, with the patient himself at the time of inclusion if not referenced in the computerized patient record or with the hospital physician in charge of the patient. These data as well as the results of the knowledge score, adherence beliefs and satisfaction surveys, the follow-up questionnaire, exploratory measures of CardioMeds usability® and self-care skills will be captured and physically stored in MySQL ver.7.x for REDCap™. An electronic clinical data management system, a CDMS (Clinical Trial Data Management System). This software is validated by the HUG clinical research center for data management.

Ongoing data from the study will be stored, queried, viewed, cleaned and exported through this CDMS.

All research subject data will be coded to ensure confidentiality using a combined letter and number identifier. The data collected for each research subject will constitute a Case Report Form (CRF), which contains the following elements

- Inclusion criteria and consent
- Demographics
- Medical data (history, co-morbidities, laboratory tests, medications)
- Knowledge, adherence and belief questionnaires in pre-test and post-test as well as satisfaction questionnaires, follow-up questionnaire, exploratory measures of CardioMeds usability® and self-care skills measures
- Questionnaire Scores
  
- Adverse events

The collection of clinical data is done through the electronic case report form (eCRF) that will be created with REDcap™.

The source documents are all the original documents related to the study, i.e. the research protocol, the ethics committee agreement, the original consent form signed by each participant and the CRF extraction. These will be stored in a study-specific file cabinet.

The identification data of the participants such as name, first name, date of birth, date of stay and any other data that can be used to identify a patient will be stored in an Excel file. This file will be stored in a computer file on the common and secured server of the HUG pharmacy. Access to this file will be strictly limited to the investigator and the file will be locked with a code accessible only by the investigator.

### 8.3 Privacy and Encryption

Trial and participant data will be treated with the utmost discretion and will be accessible only to authorized personnel who need the data to perform their duties in the study (investigator and

clinical research associate). On CRFs and other study-specific documents, participants are identified only by a unique participant number.

**Storage:**

The identification list of participants will be kept in a secure manner (see §8.2 data recording and source data)

For the duration of the study, the data will be stored in the CDMS, REDcap™, which can only be accessed by the investigator and a research assistant with a personal login and password.

All paper source data will be available in a dedicated study cabinet. This cabinet will be stored in the pharmacy's clinical trials office. All other source documents will be stored electronically, in the pharmacy's secure network, accessible only by the principal investigator and his/her research assistant.

Access to the database will be available to the study investigator and research assistant only during the inclusion process, but also during the data analysis phase and after the study is completed. Access will be password protected to prevent unauthorized access.

Once the data is collected and the REDCap™ database is complete, the data will first be extracted into an Excel spreadsheet. This will be stored in the pharmacy's secure network.

For the statistical analysis, the data of interest will be prepared for transfer to the statistician of the Methodological Support Unit, so that he can import them into the statistical software he will use. A do-file will be used to store all the statistics produced.

Where possible, we will store files in open archive formats, such as Word files converted to PDF-A or simple text files encoded as UTF-8 files and Excel files converted to CSV. If this is not possible, we will include information about the software used and its version number.

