Study procedures	
Each working day, the investigator will identify all patients with heart failure with a lowered left ventricular ejection fraction (LVEF) and hospitalized for cardiac decompensation at the HUG. He will assess whether they meet the eligibility criteria for this study. The investigator or a trained clinical research associate (CRA) will come and present the study to the eligible patients by giving them the information sheet and the consent form to sign if they agree to participate. They will be given at least 24 hours to think about whether they want to participate. Once the patients are included (eligibility criteria validated and consent signed), they will be randomly assigned to the intervention or control group according to the randomization list.
 
For patients in the intervention group, the therapeutic education intervention will be scheduled on the same day or the next day. The pre-test questionnaires (knowledge, beliefs, and adherence) will be given to them before the educational intervention. The post-test questionnaires and satisfaction survey will be given to the participants directly after the intervention. A second discharge interview will be organized shortly before final discharge from the general internal medicine or cardiology department. A call within 7

	
days of discharge will be made and an assessment at 1 month of hospitalization of the primary (knowledge) and secondary (beliefs, adherence, satisfaction, consumption of unplanned care) endpoints will be made either by e-mail, postal mail, or telephone call by the CRA only.
 
For patients in the control group, the pre-test questionnaires on knowledge, beliefs and adherence will be given to them on the same day or the day after inclusion. A post-test evaluation of knowledge, beliefs, adherence and rate of consumption of unplanned care will be performed at 1 month after hospitalization.

Study duration and Schedule	
12 months
 
Planned from 09/2022 for inclusion of first participant
 
Planned to 09/2023 for inclusion of last participant

Investigator(s)	[name] candidate, HUG Pharmacy
Study Center	
University Hospitals of Geneva
 
[name]
 
[name]

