Data privacy	
All data collected during the study will be coded to maintain confidentiality of all participants. The coding key will be accessible only by the study investigator and recorded in a protected Excel document stored on a secure server at the HUG. Data will be stored during the study using an electronic clinical data management system validated by the HUG Clinical Research Center for data management, MySQL ver.7.x for REDCap™ to which only the investigator and a trained CRA will have access. Once the study is completed, all data collected will be archived in a secure registry of the University of Geneva recognized by the CRC of the HUG.

Ethical consideration	
This study will show whether a therapeutic teaching intervention with heart failure patients carried out by a pharmacist can improve patients' knowledge and thus optimize their beliefs about medication, improve their adherence to taking them and reduce their risk of cardiac decompensation. This disease particularly affects an elderly population that is at risk of suffering from polymedication and cognitive disorders. Only patients without cognitive disorders will be included to avoid biasing the evaluation.
 
This project does not present any risk for the patient because it does not impact the therapeutic management by the medical and nursing staff.

GCP Statement	
This study will be conducted in accordance with the protocol, the current version of the Declaration of Helsinki, the ICH-GCP, the HRA, and other relevant local legal and regulatory requirements.

1  
2  
3

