Each participant will be informed that participation is voluntary and that he/she may withdraw from the study at any time. Participation in or withdrawal from the study will not affect his or her therapeutic management. They will also be informed that their medical records will be consulted by the investigating pharmacist.

All participants will receive a study information sheet and a consent form to sign in order to make an informed decision about whether or not to participate in the study (Appendix 8). The patient will be given 24 hours to decide whether or not to participate in the study. Formal consent will be obtained by collecting the consent form signed by the participant. It will be countersigned by the investigator or his representative. The consent form will be kept in the study file and a copy given to the participant. As soon as the patient's informed consent to participate is obtained, an appointment will be scheduled with the patient for the first stage of the intervention.

Each eligible participant included in the study will be assigned an authentication number in order to anonymize their data and an electronic case report form (eCRF) or observation sheet will be created.

A randomization list by random size block will be established beforehand by the HUG methodological support unit. This list will be held by the pharmacist in charge of the clinical trials, [name], within the HUG pharmacy (person external to the project). Randomization will be automated in the Clinical Trial Data Management System CDMS RedCAP™ and activated for each new participant who will require the creation of a new eCRF. In case of malfunction of this software, [name] will be notified by the system and will be able to assign each participant to the arm according to the predefined list.

The investigator will identify the assigned arm for each participant after collecting the patient consent form. The investigator will schedule the therapeutic education intervention on the same day for the participants in the intervention arm and collect the pre-test data from the participants.

Follow-up up to 1 month post-discharge involves a potential risk of loss of participants. Some may withdraw from the study. These cases will be reported as, "withdrawal of informed consent" or "loss to follow-up". Data from patients who die during the study will be considered for final data analysis.

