#### Assessment of the level of knowledge (primary outcome):

The level of knowledge of the patients will be assessed in the intervention group by a questionnaire (Appendix 1) on three occasions: at time 0 before any intervention as a pre-test, after the teaching interview as post-test n°1 and finally at 1 month post-discharge as post-test n°2.

This questionnaire will be proposed in the control group at time 0 (pre-test) and at 1 month after hospitalization (post-test).

During hospitalization, the questionnaire will be sent to the patient by the investigating pharmacist and will be completed by the patient himself with the help of the pharmacist if necessary.

At 1 month after discharge, the questionnaire will be sent to the patient by email or post. If no return is obtained, the research assistant will address the questionnaires to them during a phone call.

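### No masking of the 1-month interviewer is planned, although the assistant who makes the call can learn the arm from the database and from the call's own content

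*Combined protocol and SAP*

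**What the plan says.** **Who collects the 1-month data.** For the intervention group, the Synopsis (Study procedures) says that the assessment of primary and secondary "endpoints will be made either by e-mail, postal mail, or telephone call by the CRA only". The control-group paragraph names no assessor. For the primary outcome, section 4.3 starts with self-completion by e-mail or post and then adds: "If no return is obtained, the research assistant will address the questionnaires to them during a phone call". Beliefs and adherence follow the same route. Section 4.3 has all participants asked about readmission and unplanned visits on the 1-month call, and section 3.2 gives that call to a research assistant.

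**Who can see the database.** The Synopsis (Data privacy) describes REDCap as a system "to which only the investigator and a trained CRA will have access". Section 8.3 (Storage) repeats this: "which can only be accessed by the investigator and a research assistant with a personal login and password". A later sentence there begins "Access to the database will be available to the study investigator and research assistant only during the inclusion process" and goes on to include the analysis phase and the time after completion. Section 8.3 also makes data "accessible only to authorized personnel who need the data to perform their duties in the study", and names the clinical research associate among those personnel.

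**What the database holds.** Section 4.2: "Randomization will be automated in the Clinical Trial Data Management System CDMS RedCAP™ and activated for each new participant". Section 8.2 lists among the contents of the case report form: "Knowledge, adherence and belief questionnaires in pre-test and post-test as well as satisfaction questionnaires". Table 2 marks items 63-78 (post-interview and discharge-call data) as intervention group only.

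**What else the assistant handles.** Section 4.3 restricts satisfaction to the intervention group and has the assistant ask it by telephone if the form is not returned. It also has the assistant ask the CardioMeds usability and self-care items on the 1-month call. Section 3.2 limits those to intervention patients who installed the app, and allows the assistant to give out the in-hospital questionnaires, satisfaction included.

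**The concern.** Patients cannot be masked to a teaching session, so the 1-month interviewer is one of the few places where masking is feasible. The plan keeps the teaching pharmacist out of the intervention group's 1-month assessment but does not keep the arm from the person who takes over.

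Reading a questionnaire aloud leaves room to rephrase, repeat, prompt or wait, on closed items as well as open ones. The knowledge score is exposed to this. Section 3.2 says that the questionnaire has had no psychometric analysis, and that multiple-choice and open-ended items can earn half credit, so a small nudge on one item can move the score by 0.5. If nudging differs by arm, the difference goes straight into the primary contrast for the patients completed by telephone. Masked scoring of free text afterwards would not undo it, because the recorded answer has already changed.

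**Working it through.** The plan states no figure on this point, so the main check sets the sections side by side.

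1. **Is the interviewer also a database user?** Yes. Sections 3.2 and 4.3 give the call to the research assistant, and section 8.3 (Storage) gives the same role a REDCap login. The documents use both research assistant and CRA without saying that they are one person. The Synopsis and section 10 point to a single CRA, and I assume so.
2. **Can that database show the arm?** It can. Randomisation runs in it (section 4.2), and items 63-78 exist for one arm only (Table 2). No section describes a restricted role or hidden fields.
3. **Can the tasks show the arm without the database?** Yes. The satisfaction and CardioMeds items apply to intervention patients only, and no order of questions is set for the call.
4. **Is masking planned anywhere?** No section mentions a masked interviewer.
5. **Which outcomes are exposed?** Readmission and emergency visits for everyone. Knowledge, beliefs and adherence only for patients who did not return the forms.

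**Illustration of size.** From the plan: target difference 2.39, SD 2.67, 45 per group (section 5.1). Assumed, with no support in the documents: telephone share p = 0.30 to 0.60; one-sided gain g = 0.5 to 1.0 point (one or two half credits) in the intervention arm and none in the control arm; baseline correlation 0.5.

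- Shift in the contrast = p × g: 0.30 × 0.5 = 0.15, up to 0.60 × 1.0 = 0.60.
- As a share of the target: 0.15 / 2.39 = 6%; 0.60 / 2.39 = 25%.
- Standard error of the adjusted difference = 2.67 × √(1 − 0.5²) × √(2/45) = 0.487.
- Two-sided rejection rate with no true effect = 1 − Φ(1.96 − shift/SE) + Φ(−1.96 − shift/SE): 6.1% at a shift of 0.15 and 23.4% at 0.60, against a nominal 5%.
- Without the correlation assumption, SE = 2.67 × √(2/45) = 0.563, and the rates are 5.8% and 18.7%.

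The low end is close to nominal. The high end needs 60% by telephone and a full point of one-sided prompting for each of those patients.

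**The case against.** The strongest reply is that the documents say less than a critic might infer. Five stronger readings are tempting, and none is supported.

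- **That the assistant has unrestricted access equal to the investigator's.** Section 8.3 says who may log in, not what each login shows, and it states a need-to-know rule. The supportable statement is that no restriction is given. The rule does not supply masking either, since it names the CRA as authorised.
- **That the storage rule undoes the separation of teacher and assessor.** It does not. The pharmacist stays out of the intervention group's 1-month assessment, and since the Synopsis never promised a masked CRA, no promise is broken.
- **That database access is the decisive leak.** The intervention-only tasks reveal the arm at least as directly, and patients may mention the teaching. Restricting REDCap rights alone would not mask the caller.
- **That sight of earlier answers biases the comparison.** Pre-test answers exist in both arms, so seeing them does not by itself favour one. Among the earlier answers, only the post-interview forms reveal allocation.
- **That the bias is certain, or large.** Self-completion comes first, and 14 of the 17 knowledge items are choice questions. Readmission and emergency visits are recorded as yes/no facts, and the cause of a readmission to the trial hospital comes from its own records.

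All of this stands and narrows the point. It leaves untouched that the plan lets an interviewer who can know the arm administer the primary questionnaire by telephone, with no safeguard described.

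**Conclusion.** The point holds as an omission worth correcting: the 1-month interviewer is not masked, and both the database and the interviewer's own tasks can reveal the arm. It concerns every patient for readmission and emergency visits, and only non-returners for knowledge, beliefs and adherence.

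The size is unknown, because the documents give neither the telephone share nor any measure of interviewer effect. The 0.15-0.60 point shift shows what could happen on assumed inputs and is not an estimate for this trial. The conclusion rests on the absence of any described restriction and on the assistant and the CRA being the same role. If a restricted REDCap role is already set up, the database part falls away and the question order remains.

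**What to change.** 1. **Call order (section 4.3: knowledge, beliefs, adherence, rehospitalisation, satisfaction and app paragraphs).** State that knowledge, beliefs, adherence, readmission and emergency visits are completed and saved before any satisfaction or CardioMeds item is opened. This is the main change, since it deals with the route that database rights cannot close.
2. **Dispatch (section 3.2 and the section 4.3 satisfaction paragraph).** Have REDCap or the investigator send or hand out the intervention-only forms. REDCap is already to be set up to send the 1-month questionnaires by e-mail (note below Table 2).
3. **Access (section 8.3, Storage).** Give the 1-month interviewer a REDCap role that hides the allocation and the intervention-only forms (Table 2, items 63-78) until the outcome items are saved.

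**Cost.** User-rights settings and a fixed call script, with no extra staff. The assistant can no longer hand out intervention-only forms in hospital. Some patients will still reveal their arm, so the report should describe the masking as partial.
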